## 2.1.2 Visit windows

### 2.1.2.1 Visit windows for treatment period

Visit-windows will be used for both efficacy and safety data summaries by visit. Visit windows define a time period “around” the targeted visit date as defined in the evaluation schedule of the clinical study protocol. Visit-windows are non-overlapping and defined without gaps between consecutive visit windows. The width of visit windows may vary over the course of the study period.

Baseline assessments are defined in [Section 2.1.1](#) and do not require a visit window.

[figure not shown]
The purpose of visit windows is to analyze data based on the actual study days (rather than “nominal” visits). E.g., if a subject’s Month 1 visit is delayed; it is possible that the Month 1 data be re-aligned to visit-window Month 2 and be summarized under Month 2.

- For **efficacy analyses** all nominal visits (i.e. excluding unscheduled visits) will be mapped into one of the defined visit-windows. Note: for the derivation of disability progression all visits (scheduled and unscheduled) need to be considered before the progression can be confirmed (see [Section 2.12.1](#)).

-For **safety analyses** all visits (scheduled and unscheduled) will be mapped to visit windows.

It is possible that more than one assessment of a subject fall into a particular visit-window. [Section 2.1.2.3](#) deals with the statistical approaches to handle multiple visits in a given visit-window.

Tables displaying summary statistics “by visit” will also use the term *visit-window* as column header; this is to remind the reviewer that multiple assessments of a subject might be summarized. Below tables provide visit-windows definitions for applicable parameters.

**Table 2-3 Visit-windows for MRI**

Visit-window	Start day	Target Day	End day
Month 3	1	84	210
Month 12	211	336	462

**Table 2-4 Visit-windows for routine laboratory values**

Visit-window	Start day	Target Day	End day
Month 1	1	28	56
Month 3	57	84	126
Month 6	127	168	210
Month 9	211	252	294
Month 12	295	336	378
Month 15	379	420	462

**Table 2-5 Visit-windows for vital signs\***

Visit-window	Start day	Target Day	End day
Month 1	1	28	56
Month 3	57	84	126
Month 6	127	168	210
Month 9	211	252	294
Month 12	295	336	378
Month 15	379	420	462

\*Data collected from Day 1 protocol scheduled visit will not be mapped to the visit windows due to different data collection on those visits.

**Table 2-6 Visit-windows for B-cell counts**

Visit-window	Start day	Target Day	End day
Month 1	1	28	56
Month 3	57	84	126

Month 6	127	168	252
Month 12	253	336	420

**Table 2-7 Visit-windows for IgG and IgM**

Visit-window	Start day	Target Day	End day
Month 6	1	168	252
Month 12	253	336	420

### 2.1.2.2 Visit windows after study drug discontinuation

For summaries of data collected after study drug discontinuation, data from both Treatment period and Post-treatment Follow-up period will be considered. All reporting will be done based on visit windows defined relative to the last administration of study drug.

The visit window definitions are provided in [Table 2-8](#) where the Start day and End day are relative to the date of last administration of study drug. For the “Last assessment on drug”, the last assessment with non-missing value taken before or on the date of last administration of study drug will be summarized (no visit window applies). For the “Month 3 after LDD (last dose date)” visit-window, assessments taken at least 1 day after but no more than 126 days after the date of last administration of study drug will be considered. LDD stands for last dose date and will be footnoted in applicable output(s).

**Table 2-8 Visit-windows after study drug discontinuation**

Visit-window	Start day	Target Day	End day
Last assessment on drug	NA	NA	NA (see above or Section 2.1.1 )
Month 3 after LDD	2	84	126
Month 6 after LDD	127	168	210
Month 9 after LDD	211	252	294
Month 12 after LDD	295	336	378
Month 15 after LDD	379	420	462

### 2.1.2.3 Multiple assessments within visit windows

It is possible that multiple assessments of a subject fall into the same visit-window (e.g. due to unscheduled visits). All results (scheduled and unscheduled) will be displayed in listings, but only one value (observed or derived) will be selected for summary statistics by visit-window. If multiple unscheduled visits within visit window are allocated to the same missed scheduled visit:

For **quantitative variables**, the unscheduled assessment closest to the target day will be selected. If more than one assessment is at the same distance to the target day, the later one will be selected. For tables displaying the worst case scenario, such as notable abnormalities, all assessments within a visit window will be used to identify the worst (e.g. the maximum or the

minimum depending on parameter). Where applicable it will be defined for each parameter what the worst case is.

For **qualitative variables**, the worst record is selected; it is noted that in the relevant data subsection, worst case is always well defined.

Note that “Last assessment on study drug” is the last observation while the subject is on study drug. Therefore, the above multiple assessment rules do not apply.

## **2.2 Analysis sets**

**The Full Analysis Set (FAS)** comprises all participants who have signed the Informed Consent and who have received at least one dose of study treatment. The FAS will be used for the summary of demography and baseline characteristics as well as for all efficacy analyses.

**The Safety Set (SAF)** is identical to FAS in this study. The Safety Set will be used for all safety analyses.

**The screened subjects (SCR) set** comprises all subjects who have signed the Informed Consent and were screened.

## **2.3 Patient disposition, demographics and other baseline characteristics**

### **2.3.1 Patient disposition**

The number and percentage of subjects who were screened but did not continue into the Treatment Period will be presented, along with the reason for discontinuation being “Screen Failure”. Data collected on the Disposition CRF page will be used to summarize this information. The summary will be on the SCR set.

The number and percentage of subjects who completed the study (i.e. the Treatment Period) or prematurely discontinued the study prior to the end of the treatment period will be presented, along with the primary reason for discontinuation. Data collected on the Study disposition CRF page will be used to summarize this information. The summary will be on the FAS. Subjects who prematurely discontinue the study will also be listed along with the reason for discontinuation. Similar summary will also be provided for the Post-treatment Follow-up period based on the FAS and data collected on the Post treatment follow-up disposition CRF.

Protocol deviations will be summarized by deviation categories for the FAS. In addition, protocol deviations that led to exclusion from the analysis set will be listed.

### **2.3.2 Demographics and other baseline characteristics**

#### **2.3.2.1 Background and demographic characteristics**

All analyses in this section will be presented on FAS.

Background characteristics include subject demographic characteristics (sex, race and ethnicity collected on the Demography CRF), age at screening, height, body weight and BMI at baseline.

Age, baseline height, body weight and derived BMI will be presented. These variables will be summarized for the FAS using frequency distributions (for categorical variables) and descriptive statistics of mean, standard deviation, minimum, median and maximum (for continuous variables).

### **2.3.2.2 MS baseline disease characteristics**

All analyses in this section will be presented on FAS.

MS baseline characteristics, MS disease history and MS medication history will be summarized for the FAS.

MS baseline characteristics include baseline EDSS and key MRI parameters (e.g., number of Gd-enhancing T1 lesions and T2 lesion volume).

MS disease history includes duration of MS since diagnosis (years), duration of MS since first symptom (years), number of relapses in the last 12 months prior to screening, number of relapses in the 12 to 24 months prior to screening, and time since onset of most recent relapse (months) prior to screening.

Duration of MS since diagnosis (years) will be derived as  $[(\text{first dose date} - \text{MS diagnosis start date} + 1) / 365.25]$ . Duration of MS since first symptom (years) will be derived as  $[(\text{first dose date} - \text{first MS symptom date} + 1) / 365.25]$ . Time since onset of most recent relapse (months) will be derived as  $[(\text{first dose date} - \text{most recent relapse onset date} + 1) / (365.25 / 12)]$ . In these calculations, partial dates (if any) will be imputed according to the rules specified in [Section 5.1.4.1](#).

MS medication history of previous disease-modifying drugs (coded by World Health Organization (WHO) drug dictionary) will be summarized by preferred term (PT). The number and proportion of treatment-naïve subjects (i.e. subjects who have not been treated with any disease-modifying drug before study enrollment) will also be presented.

### **2.3.2.3 Medical history**

Medical history will be summarized on the FAS. Any condition entered on the Medical History CRF will be coded using the Medical Dictionary for Drug Regulatory Affairs (MedDRA) dictionary. The medical history will be summarized by primary system organ class (SOC) and preferred term.

Relevant medical histories and current medical conditions at baseline will be summarized by system organ class and preferred term.

## 2.4 Treatments (study treatment, rescue medication, concomitant therapies, compliance)

### 2.4.1 Study treatment / compliance

The summary of exposure and time-at-risk will be based on the SAF.

**Duration of exposure to study drug** expressed in days is defined as the number of days spent on study treatment. Intermediate treatment interruptions will be subtracted from drug exposure, i.e. the duration of exposure to study treatment (in days) will be calculated as (last injection date – first injection date + 31 –  $\Sigma [(j+1)^{\text{th}} \text{ injection date} - j^{\text{th}} \text{ injection date} - 31]$ ), where j and j+1 refer to consecutive injections with injection dates more than 31 days apart.

Exposure to investigational study drug will be summarized with number and percentage of subjects by time category, and with summary statistics of the number of patient years of exposure.

Duration of exposure to study treatment will be summarized descriptively by duration category (i.e.  $\geq 1$  month,  $\geq 3$  months,  $\geq 6$  months,  $\geq 9$  months,  $\geq 12$  months). Descriptive statistics of duration in days will also be provided. The number of patient years is calculated as the sum of the duration of exposure for all subjects in the group.

**Time at risk** is the censoring time used for participants who did not experience the event of interest. For participants who have experienced the event of interest, the actual date of the SAE, or AE onset will be used.

- **Time at risk for AE** is defined as the number of days spent in the study, from first to last administration of study drug, plus the safety data cut-off of 100 days (or until EOS for participants continue with commercial ofatumumab immediately after EOS, or until last dose of study medication plus 100 days or one day before switching to another DMT, whichever comes earlier, for participants who have such switch in the PT FU). Time at risk for AE will be used for tables reporting AEs (including both SAE and non-SAE).
- **Time at risk for SAE** is defined as the number of days spent in the study from the day of first administration of study drug to the end of Post-treatment Follow-up period if the participant does not continue with commercial ofatumumab immediately after EOS. Time at risk for SAE will be used only for tables reporting SAEs.

Time at risk for AE and time at risk for SAE will be summarized in a similar way to duration of exposure to study drug.

**Compliance to the study treatment administration schedule** will be calculated as duration of exposure to study treatment in (days) / duration of on-treatment period (as defined in [Table 2-1](#)) (in days)  $\times 100\%$ . This rule means that compliance will be measured during the time interval the subject took study treatment, i.e. premature discontinuation from study treatment will not be considered non-compliance. Compliance to study treatment administration will be summarized descriptively on the SAF. In addition, compliance will be summarized with cumulative number and percentage of subjects in each compliance category (i.e.  $\geq 20\%$ ,  $\geq 30\%$ ,  $\geq 40\%$ ,  $\geq 50\%$ ,  $\geq 60\%$ ,  $\geq 70\%$ ,  $\geq 80\%$ ,  $\geq 90\%$ ,  $\geq 95\%$ ,  $\geq 98\%$ ,  $= 100\%$ ).

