6.1.3 Treatment arms

This is an open-label study with one treatment arm (ofatumumab 20 mg s.c. injections at Week 0, Week 1, Week 2, Week 4 and every month thereafter).

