6.3.2 Instruction for prescribing and taking study treatment

Ofatumumab will be dispensed starting at W0, and then at scheduled visits throughout the Treatment period according to [Table 8-1](#).

Participants will receive 3 initial s.c. injections of ofatumumab at W0, W1 and W2, followed by subsequent regular monthly dosing starting at W4 (a month is defined as 28 days).

The first s.c. injection at W0 will be administered [REDACTED]

[REDACTED]

[REDACTED]

Participants, who miss s.c. injections or temporarily interrupt study drug without discontinuing from the study or withdrawing consent, will be permitted to resume study drug if determined to be safe and appropriate in the opinion of the Investigator. When resuming study drug, the timing of the next s.c. injection will be determined based on the original study schedule as follows:

- If one monthly injection is missed by more than 1 week, the participant should skip the dose and take the next dose at the time when the next injection would be due according to the original schedule.
- If two or more consecutive monthly injections are missed, the Investigator should inform the local Sponsor Medical Advisor before re-starting dosing.
- If any initial dose (at W0, W1 or W2), or the W4 dose is missed, then the injection should be administered as soon as possible. The next injection should then be administered according to the original schedule.

All dosages prescribed to the participant and all dose administrations and interruptions during the study must be recorded on the eCRF.

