**Table 2-1 General definitions**

Study treatment/Study drug	The investigational drug (ofatumumab) will be referred as study treatment or study drug.
Date of first administration of study drug/first dose date	The first dose date of active study drug (ofatumumab) administration.
Date of last administration of study drug/last dose date	The last dose date of active study drug (ofatumumab) administration.

Study Day 1 or Day 1	The date of first administration of study drug/first dose date.
Study Day	All other study days will be labeled relative to Day 1. For events with dates on or after Day 1, study day for the event is calculated as (event start date – first dose date + 1). For events with dates before Day 1, study day for the event is calculated as (event start date – first dose date).  Day 0 will not be used.
Duration of an event	Duration of an event is calculated as (event end date – event start date +1).
1 month	30 days; to be used in defining 3-month confirmed disability progression.
4 weeks	28 days; to be used in determining target days of scheduled visits. It is based on the scheduled injection frequency for ofatumumab (during the maintenance phase).
Day post-study drug discontinuation	Day post-study drug discontinuation for a particular event is calculated as (event start date – study drug discontinuation date).
Baseline	Baseline is the last assessment with non-missing value obtained prior to the first administration of study drug. No visit windows will be needed for the identification of baseline assessment.  For pulse and blood pressure vital sign values, if 3 measurements were taken on the last visit prior to the first administration of study drug, then the baseline is the average of the non-missing values of them.
On-treatment period	For participants received ofatumumab, on-treatment period includes days from the first injection date until 30 days after the last injection date. The on-treatment definition applies to efficacy analyses and B-cell summaries only.  For calculation of compliance to study drug administration, similar definition of on-treatment period will be used.

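### The SAP 2.4.1 compliance measure cannot register an omitted Week 1 or Week 2 injection, so a participant who missed either or both can be counted as 100% compliant

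*SAP*

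**What the plan says.** SAP 2.4.1 calls the measure "Compliance to the study treatment administration schedule". It "will be calculated as duration of exposure to study treatment in (days) / duration of on-treatment period", times 100%. Three definitions feed it:

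- **Numerator.** Exposure in days is last minus first injection date plus 31, less the part of any interval beyond 31 days. The subtraction applies only "where j and j+1 refer to consecutive injections with injection dates more than 31 days apart".
- **Denominator.** SAP Table 2-1 states that the "on-treatment period includes days from the first injection date until 30 days after the last injection date", and adds: "For calculation of compliance to study drug administration, similar definition of on-treatment period will be used".
- **Schedule.** Protocol 6.1.3 gives the single arm as "ofatumumab 20 mg s.c. injections at Week 0, Week 1, Week 2, Week 4 and every month thereafter". Protocol 6.3.2 sets a month at 28 days, and Protocol Table 8-1 schedules no injection at Month 12.

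SAP 2.4.1 states one limit on what the measure covers: stopping treatment early does not count against the participant. It does not mention the initial doses. The result is summarized descriptively on the safety set and by cumulative categories, the highest being exactly 100%.

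**The concern.** The 31-day allowance suits monthly dosing. The first injections are 7, 7 and 14 days apart, and the whole stretch from Week 0 to Week 4 fits inside one allowance. The doses between those two points therefore have no influence on the score.

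The label promises compliance with the administration schedule, and Weeks 1 and 2 are part of that schedule. Protocol 6.3.2 foresees that an initial dose may be missed and gives such doses their own handling rule. The SAP plans no other table that counts injections received or shows adherence to the initial doses. What is at stake is whether this one table describes delivery of the regimen as its label says.

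**Working it through.** The documents give no compliance figure to reproduce, so the check applies the SAP formula to the protocol schedule.

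**Inputs**

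- Scheduled injection days, counting Week 0 as day 0: 0, 7, 14, then 28, 56, ..., 308 (Months 1 to 11). That is 3 + 11 = 14 injections (Protocol 6.1.3, 6.3.2, Table 8-1).
- Exposure = (last − first + 31) − Σ(gap − 31), summed over gaps above 31 days (SAP 2.4.1).
- On-treatment days = last − first + 30 + 1 = last − first + 31, using the inclusive day count of SAP Table 2-1.
- Compliance = exposure / on-treatment days × 100%.

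**Baseline check.** With every dose on schedule, the longest gap is 28 days, so nothing is subtracted. Exposure is 308 + 31 = 339, on-treatment days are 339, and compliance is 100%. The formula is right for a fully adherent participant.

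**Missed doses, all others on schedule**

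| Omitted | Longest gap (days) | Subtracted | SAP formula | Injections received |
|---|---|---|---|---|
| Week 1 or Week 2 | 28 | 0 | 339/339 = 100% | 13/14 = 92.9% |
| Weeks 1 and 2 | 28 | 0 | 339/339 = 100% | 12/14 = 85.7% |
| Week 4 | 42 | 11 | 328/339 = 96.8% | 13/14 = 92.9% |
| Weeks 1, 2 and 4 | 56 | 25 | 314/339 = 92.6% | 11/14 = 78.6% |
| Month 6 | 56 | 25 | 314/339 = 92.6% | 13/14 = 92.9% |
| Months 5 and 6 | 84 | 53 | 286/339 = 84.4% | 12/14 = 85.7% |

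For mid-study monthly doses the formula stays close to the dose count. For Weeks 1 and 2 it does not move.

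**Conditions for the 100%.** With Weeks 1 and 2 omitted and Week 4 given late, the score stays at 100% up to day 31. It becomes 338/339 = 99.7% at day 32 and 335/339 = 98.8% at day 35. Those losses come from the late Week 4 dose, which creates a gap above 31 days; the omitted doses themselves never enter the calculation.

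**Early stop.** A participant who received only Week 0 and Week 4, 2 of the 4 injections due by then, has 28 + 31 = 59 exposure days over 59 on-treatment days, again 100%.

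**Day-count convention.** A non-inclusive denominator gives 339/338 = 100.3% both for the fully adherent participant and for the one without Weeks 1 and 2. The two remain indistinguishable.

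**The case against.** The strongest reply is that the SAP makes no calculation error. It openly defines compliance as time covered, and that measure responds to every missed monthly dose that is followed by another injection, and to monthly injections late enough to leave a gap above 31 days. A plain dose count ignores timing: a Week 1 dose on day 13 counts the same as one on day 7. This stands, and it is a reason to keep the formula and add to it.

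Protocol 6.3.2 also asks for a missed initial dose to be given as soon as possible, with the next injection on the original schedule. A participant handled that way may still receive 14 of 14. The case here needs the dose never to be given at all. This stands too, and it limits how often the problem can arise.

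Nor are the data lost. Protocol section 8 provides a telephone interview for the Week 1 and Week 2 doses and a diary of injection dates and times, and Protocol 6.3.2 requires all administrations to be recorded on the eCRF. SAP 2.3.1 summarizes protocol deviations by category, though the documents do not say that a missed initial dose has its own category. None of this changes what the compliance table would show.

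A reader might infer that the compliance results are wrong in general, or that the efficacy result is affected. The documents support neither. The formula is correct for participants who took every dose. The analysis sets require only one dose (SAP 2.2), and the primary model in SAP 2.5.2 has no compliance term.

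**Conclusion.** The point holds as a blind spot covering two of the 14 scheduled injections. A participant who never receives Week 1, Week 2 or both is placed in the 100% category after 92.9% or 85.7% of scheduled injections, provided that Week 4 falls within 31 days of Week 0 and no later gap exceeds 31 days. This assumes that the denominator for compliance, which SAP Table 2-1 calls similar, is the on-treatment period as defined there.

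How many participants are affected cannot be derived from the documents and may be small. The effect on an average is slight: with about 100 participants, each one who omits both doses would lower a mean dose-count compliance by 14.3/100 = 0.14 percentage points. The 100% category is the most exposed output. This is a minor point about a descriptive safety-set table.

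**What to change.** In SAP 2.4.1:

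- Keep the exposure-days formula, and label it as time coverage.
- Add a summary of injections received divided by injections scheduled up to and including the participant's last injection. This keeps the SAP's position that stopping early is not non-compliance. The denominator should be defined that way and not fixed at 14 for completers: someone who misses only the Month 11 dose would be 13/13 when counting up to the last injection and 13/14 = 92.9% with a fixed 14.
- Show the initial doses (Weeks 0, 1, 2 and 4) separately, received against scheduled.
- State that a late catch-up dose counts as received.

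The cost is SAP wording and one more derivation. No new data are needed, since administrations are on the eCRF and SAP 5.1.1 does not allow missing or partial dates on the study treatment pages. Reported compliance may be slightly lower than under the present measure.
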